NON-INTERVENTIONAL STUDY (NIS) PROTOCOL

Study information

Title	Treatment patterns and outcomes in patients treated with BeneFIX or ReFacto/ReFacto AF – A Swedish cohort study
Protocol number	B1821054
Protocol version identifier	1
Date of last version of protocol	16 June 2015
Active substance	B02BD09 - nonacog alfa B02BD02 - moroctocog alfa
Medicinal product	BeneFIX, ReFacto/ReFacto AF
Research question and objectives	The objective of this study is to describe demographic and clinical characteristics, treatment patterns and outcomes, as well as the related treatment costs in the populations of hemophilia patients treated with BeneFIX and ReFacto/ReFacto AF at the Malmö Hemophilia Center. The analyses will be carried out for the total populations and for subgroups (e.g. level of severity).
[name] Health Economics Manager Medical GIP and Health & Value, Pfizer AB [name] Tel: PPD Email: PPD

TABLE OF CONTENTS

1. LIST OF ABBREVIATIONS.....	3
2. RESPONSIBLE PARTIES.....	4
3. AMENDMENTS AND UPDATES.....	5
4. MILESTONES.....	6
5. RATIONALE AND BACKGROUND.....	6
6. RESEARCH QUESTION AND OBJECTIVES.....	8
7. RESEARCH METHODS	9
7.1. Study design	9
7.2. Setting.....	9
7.3. Exclusion criteria.....	10
7.4. Variables.....	10
7.5. Data sources	12
7.6. Study size	12
7.7. Data management.....	12
7.8. Data analysis	13
7.9. Quality control.....	13
7.10. Limitations of the research methods	14
7.11. Other aspects	14
8. PROTECTION OF HUMAN SUBJECTS	14
8.1. Patient Information and Consent.....	14
8.2. Patient withdrawal.....	14
8.3. Institutional Review Board (IRB)/Independent Ethics Committee (IEC)	14
8.4. Ethical Conduct of the Study	15
9. MANAGEMENT AND REPORTING OF ADVERSE EVENTS/ADVERSE REACTIONS	15
10. PLANS FOR DISSEMINATING AND COMMUNICATING STUDY RESULTS.....	15
11. COMMUNICATION OF ISSUES	17
12. REFERENCES	17
ANNEX 1. LIST OF STAND ALONE DOCUMENTS	18
ANNEX 2. ADDITIONAL INFORMATION.....	18

1. LIST OF ABBREVIATIONS

Abbreviation	Definition
ICD-10	International Statistical Classification of Diseases and Related Health Problems - Tenth Revision
IEC	Independent Ethics Committee
IHE	Swedish Institute for Health Economics
IRB	Institutional Review Board
NBHW	National Board of Health and Welfare
MHC	Malmö Hemophilia Center
MHR	Malmö Hemophilia Registry
NIS	Non-Interventional Study
PIN	Personal Identification Number
SAP	Statistical Analysis Plan
SUH	Skåne University Hospital

3. AMENDMENTS AND UPDATES

None

4. MILESTONES

Milestone	Planned date
Start of data collection	01 August 2015
End of data collection	31 September 2015
Final study report	31 November 2015
Publication submitted	31 December 2015

5. RATIONALE AND BACKGROUND

In Sweden nearly 950 people suffer from bleeding disorders. Of these individuals, about 900 are diagnosed with hemophilia A (insufficient production of coagulation factor VIII) and B (insufficient production of coagulation factor IX). The distribution of patients with hemophilia A and B is about 80 percent and 20 percent respectively. About 50 people are diagnosed with von Willebrand disease [1]. All these patients lack sufficient levels of a protein in the blood that impacts the coagulation process. As a result the patients have a higher risk of having a bleed as well as suffer from prolonged bleeding. Bleeding can result in severe complications, especially in joints, and could result in permanent damage such as pain and disability [2].

Patients diagnosed with coagulation disorders receive intravenous replacement treatment of the missing coagulation factor. Replacement treatment can be given prophylactically, i.e., regularly to reduce the insufficiency to prevent bleeding to occur. It can also be given when a bleed occurs with the aim to stop the bleed and/or to stop it from becoming more severe, i.e., on demand treatment. The type of replacement treatment may depend on the severity of the disease [2].

At the Malmö Hemophilia Center (MHC) in Sweden patients diagnosed with bleeding disorders have been treated prophylactically since 1958. The treatment has intensified over time and today patients at the MHC, as well as Swedish patients in general, are treated from

the age of 1-3 years [2]. Injections with replacement treatment for hemophilia A is generally given three to four times a week and for hemophilia B twice a week, when the disease is severe. The patients that belong to the MHC are well monitored - their treatments and outcomes have been registered in the Malmö Hemophilia Register (MHR) since 1977. The MHR therefore represents the best available source of information on treatments and outcomes of hemophilia in Sweden.

The first type of treatment available for Hemophilia A and B had a low percentage of coagulation factors and blood borne viruses such as Hepatitis C and HIV could be transferred to the patient. In the 1990's products that were produced using gene technology, recombinant products, with no risk of blood borne viruses, came to the market. Today several such products, among them ReFacto that was introduced in 1999 (ReFacto AF in 2009), exist for treatment of hemophilia A and most patients are treated with recombinant products [2, 3]. For treatment of hemophilia B four different replacement treatments exist and one of them (BeneFIX) is produced using gene technology [4]. In the US products with extended half-life, that make less frequent dosing possible, are available. These products are expected to be available in the European market in the end of 2015/early 2016.

The aim of this study is to analyze the real world use of BeneFIX and ReFacto/ReFacto AF in hemophilia patients in Sweden. Sweden has a long tradition of population-based research within many therapeutic areas. Information in different registers can be record-linked by using the Swedish Personal Identification Number (PIN) that is unique to each Swedish citizen. The information available in the MHR linked together with information on treatments prescribed and picked up at the pharmacy, available in the Swedish prescription register, (held by the National Board of Health and Welfare, NBHW) provide a unique opportunity to provide in depth knowledge on actual treatment patterns and outcomes for patients diagnosed with hemophilia.

To our knowledge, no study to date has addressed in detail treatment outcomes, prescription patterns, actual treatment patterns, and the associated costs in a cohort of patients with coagulation disorders that are treated with BeneFIX or ReFacto/ReFacto AF. Previous

research that has looked at treatment of hemophilia has e.g. focused on differences between the treatment regimens and the associated outcomes, see e.g. Berntorp et al (2012) for a review of such articles [5]. Recent research based on Swedish data investigates the long-term outcomes in hemophilia patients [6]. Previous research has also focused on real world treatment and outcomes in patients with inhibitors (see e.g. Osooli M et al (2015) for a systematic review of reasons for inhibitors and on what registries around the world have contributed to the learnings about inhibitors) [7-9]. Previous research has also focused on the HRQoL of hemophilia patients) [10].

6. RESEARCH QUESTION AND OBJECTIVES

This study is explorative, i.e., not hypothesis driven. The overall aim of the study is to describe demographic and clinical characteristics, treatment patterns and outcomes, as well as the related direct treatment costs in the populations of hemophilia patients treated with BeneFIX and ReFacto/ReFacto AF, and in subgroups (e.g. level of severity) at the MHC in Sweden.

In more detail the primary objectives are:

- To describe basic demographic and clinical characteristics
- To describe prescription patterns, actual treatment patterns, and the relative dose intensity
- To describe treatment outcomes such as bleed and joint damage
- To study the relationship between bleed and actual treatment patterns
- To describe the use of replacement treatment administered in hospital in connection with invasive procedures

The secondary objectives are:

- To describe the costs associated with the prescription and actual treatment patterns
- To describe the costs associated with replacement treatment administered in hospitals

Patients that develop inhibitory antibodies will be included but analyzed separately.

7. RESEARCH METHODS

Methodology for the statistical analyses will be detailed in a statistical analysis plan (SAP).

7.1. Study design

The study will be carried out as a retrospective population-based register study. Detailed data for each patient diagnosed with hemophilia treated at the Skåne University Hospital (SUH) is collected in the MHR. The hemophilia patients treated at the SUH represent approximately 40 percent of the Swedish hemophilia population. The information in the MHR will be complemented with information from medical records. Information on drugs will be obtained from the Prescribed Drug Registry held by the NBHW. The information from the different sources will be record-linked at the MHC using the Swedish PINs that are unique to each Swedish citizen

The main strength of this study is that we are able to analyze the questions described in section 6. in a population-based setting.

7.2. Setting

The study population will consist of all patients diagnosed with hemophilia (D66.9 (hemophilia A) D67.9 (hemophilia B) in International Statistical Classification of Diseases and Related Health Problems (ICD-10) that have been registered in the MHR since 1977 and that have had at least one registered prescription of BeneFIX or ReFacto/ReFacto AF in the MHR since market authorization of the respective product (Benefix August 27 1997, ReFacto April 13 1999, ReFacto AF July 1 2009). Diseased individuals are included.

Information on drugs picked up at the pharmacy is available in the Prescribed Drug Register in from 2005.

7.3. Exclusion criteria

There are no exclusion criteria for this study.

7.4. Variables

Background information		
Variable	Data source(s)	Description
Year of birth	Malmö Hemophilia Register	
Year of diagnosis	Malmö Hemophilia Register	
Year of death	Malmö Hemophilia Register	
Age at treatment start	Malmö Hemophilia Register	In months
Sex	Malmö Hemophilia Register	1 = man, 2 = woman
Inhibitor status	Malmö Hemophilia Register	Current, ever, never
Disease severity	Malmö Hemophilia Register	Mild, moderate, severe
Type of bleeding disorder	Malmö Hemophilia Register	ICD-10 codes
Hepatitis C antibody infected	Malmö Hemophilia Register	1 = yes, 2 = no
HIV positive	Malmö Hemophilia Register	1 = yes, 2 = no
Yearly information		
Variable	Data source(s)	Description
Prophylactic treatment	Malmö Hemophilia Register	1 = yes, 2 = no
Body weight	Malmö Hemophilia Register	In kilogram at yearly evaluation
Traumatic Bleed joint	Malmö Hemophilia Register/Clinical records	Number of bleeds at yearly evaluation

Spontaneous bleed joint	Malmö Hemophilia Register/Clinical records	Number of bleeds at yearly evaluation
Traumatic bleed soft tissue	Malmö Hemophilia Register/Clinical records	Number of bleeds at yearly evaluation
Spontaneous bleed soft tissue	Malmö Hemophilia Register/Clinical records	Number of bleeds at yearly evaluation
Intracranial bleed	Malmö Hemophilia Register/Clinical records	Number of bleeds at yearly evaluation
Gastrointestinal bleed	Malmö Hemophilia Register/Clinical records	Number of bleeds at yearly evaluation
Urinary tract bleed	Malmö Hemophilia Register/Clinical records	Number of bleeds at yearly evaluation
Joint score Gilbert (World Federation of Hemophilia Physical Examination Score)	Malmö Hemophilia Register	Available until 2008/09
Joint score HJHS	Malmö Hemophilia Register	Hemophilia Joint Health Score (HJHS)(0-143) (Available from 2008/09)
Surgery in joint for hemophilia related problems	Clinical records	For each surgery information on year of surgery and surgery type, treatment type and number of units
	Information on drug prescription	
Prescribed dose per infusion	Malmö Hemophilia Register	IU,U,µg
Prescribed dose per kilogram	Malmö Hemophilia Register	IU,U,µg
Prescribed frequency of infusion	Malmö Hemophilia Register	The weekly number of infusions, range from when needed to daily
Annual consumption of factor concentrate	Malmö Hemophilia Register	Patient reported consumption during calender year
Information related to each drug expedition		
Variable	Data source(s)	Description
Product prescribed	The Prescribed Drug Register	ATC codes
Prescription date	The Prescribed Drug Register	Year month day

Expedition date	The Prescribed Drug Register	Year month day
Dosage text	The Prescribed Drug Register	
Product identification number or package size (Number of IU)	The Prescribed Drug Register	
Number of expedited units	The Prescribed Drug Register	
Apris (AIP)	The Prescribed Drug Register	
Ppris (AUP)	The Prescribed Drug Register	

7.5. Data sources

Individual data will be extracted from the MHR and supplemented with information on surgery and/or bleed episodes from medical records when deemed necessary. Information on drugs prescribed and picked up from the pharmacy come from the prescribed drug register at the NBHW. The information from the different sources will be record-linked at the MHC by using the Swedish PINs that are unique to each Swedish citizen.

7.6. Study size

The register that will be used for this study contains information on all Swedish patients diagnosed with hemophilia that are treated at the MHC since 1977. The MHC is one of three hemophilia centers in Sweden and is responsible for treating about 40 percent of the Swedish hemophilia population. The approximate number of patients in the register that are relevant for this study amount to about 40 patients for BeneFIX and 20 patients for ReFacto/ReFacto AF .

7.7. Data management

Data from the MHR and from the NBHW will be record linked and all PIN will be replaced by patient study numbers, before they are sent to the vendor, the Swedish Institute for Health Economics (IHE). Data management at IHE will include quality and consistency checks. All corrections and editing will be tracked for transparency. All data storage and analyses will be carried out in statistical software Stata 13.0 or later versions.

7.8. Data analysis

All data will be displayed using standard statistical methods. Outcomes will be measured using a lifetime perspective while treatment patterns and associated costs will be analyzed using shorter time periods. Descriptive statistics will be carried out using frequency and percentage for categorical variables and mean, standard deviation, median, min and max for continuous variables.

Detailed methodology for summary and statistical analyses of data collected in this study will be documented in a SAP, which will be dated, filed and maintained by the sponsor. The SAP may modify the plans outlined in the protocol; any major modifications of primary endpoint definitions or their analyses would be reflected in a protocol amendment.

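### Section 7.8 gives outcomes a lifetime window and sets no on-product period, so bleeds reported for the BeneFIX and ReFacto/ReFacto AF cohorts can include years before or off the product

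*Protocol*

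**What the plan says.** The time window is set in Protocol section 7.8: "Outcomes will be measured using a lifetime perspective while treatment patterns and associated costs will be analyzed using shorter time periods". The shorter periods are not specified.

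Section 7.2 takes hemophilia patients registered at the Malmö center since 1977 "that have had at least one registered prescription of BeneFIX or ReFacto/ReFacto AF in the MHR since market authorization of the respective product". The authorization dates given are 27 August 1997 (BeneFIX), 13 April 1999 (ReFacto) and 1 July 2009 (ReFacto AF). Section 7.3 has no exclusions. On pharmacy data, 7.2 adds: "Information on drugs picked up at the pharmacy is available in the Prescribed Drug Register in from 2005".

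The primary objectives in section 6 include "To describe treatment outcomes such as bleed and joint damage" and "To study the relationship between bleed and actual treatment patterns". In section 7.4 each bleed variable is recorded as "Number of bleeds at yearly evaluation".

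Section 7.8 allows the SAP to modify the plan, but adds that "any major modifications of primary endpoint definitions or their analyses would be reflected in a protocol amendment".

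**The concern.** The study is about outcomes in patients treated with two named products. One prescription puts a patient in a product cohort, and the lifetime window then brings in the whole recorded bleed history, whatever the patient was receiving at the time. The protocol itself gives reason to think those earlier years differ: section 5 says of care at the center that "The treatment has intensified over time". A lifetime bleed summary can therefore mix treatment eras, and a reader would probably take it as bleeding on BeneFIX or ReFacto.

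There is a second, weaker risk. The objective relating bleeds to actual treatment has two sides, and the only windows stated for them differ: lifetime for bleeds, shorter for treatment. The protocol does not say that lifetime bleeds will be related to short-window treatment. If those windows were carried over, bleeds and treatment would come from different years.

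Section 7.10 does not warn of either. For bleeding it mentions self-report and the small number of events, not the time window.

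**Working it through.** The protocol has no figure to reproduce: the study is exploratory, and the 40 and 20 patients in 7.6 are approximate register counts. Two checks apply.

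**1. Does any other section restrict the window?** Section 7.2 sets cohort entry but no index date. Section 7.3 excludes nobody. The only start variable in 7.4 is age at treatment start, which is not tied to a product. The Malmö register prescription rows in 7.4 list dose, frequency and annual consumption, but neither product nor date. Nothing in the protocol assigns bleed years to a product or ends follow-up at a switch. The lifetime statement in 7.8 therefore stands unqualified.

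**2. How much register time can precede the product?** Inputs are the authorization dates in 7.2, the 1977 start of the register, and an assumed end of follow-up on 1 August 2015 (the planned start of data collection in section 4). Registration years are illustrative. ReFacto's date is used for the combined ReFacto/ReFacto AF cohort.

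Share before product = (product date − registration date) / (end date − registration date), in days/365.25, set to zero if negative.

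For registration on 1 January 1977 and BeneFIX: 20.65 / 38.58 = 53.5%. For 31 December 1977: 19.66 / 37.58 = 52.3%. The other cells are computed in the same way; each pair is registration on 1 January / 31 December.

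| Registered | Register time (y) | Before BeneFIX authorization | Before ReFacto authorization | Before an assumed product start on 1 Jan 2005 |
|---|---|---|---|---|
| 1977 | 38.58 / 37.58 | 20.65 / 19.66 y (53.5% / 52.3%) | 22.28 / 21.28 y (57.7% / 56.6%) | 28.00 / 27.00 y (72.6% / 71.9%) |
| 1987 | 28.58 / 27.58 | 10.65 / 9.66 y (37.3% / 35.0%) | 12.28 / 11.28 y (43.0% / 40.9%) | 18.00 / 17.00 y (63.0% / 61.6%) |
| 1997 | 18.58 / 17.58 | 0.65 / 0 y (3.5% / 0%) | 2.28 / 1.28 y (12.3% / 7.3%) | 8.00 / 7.00 y (43.1% / 39.8%) |
| 2005 | 10.58 / 9.58 | 0 | 0 | not applicable |

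Ending at 30 September 2015 instead barely changes this: for registration on 1 January 1977 the shares are 53.3% (BeneFIX) and 57.5% (ReFacto).

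**What this could do to a bleed rate.** The protocol gives no bleed rates, so these are assumed.

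Lifetime rate = (pre-product rate × pre-product years + on-product rate × on-product years) / total years.

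Take 1 bleed per year over 10 on-product years:

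- Pre-product rate 1: the lifetime rate is 1.0 whatever the number of pre-product years.
- Pre-product rate 2: from (2×5 + 10)/15 = 1.33 with 5 pre-product years to (2×20 + 10)/30 = 1.67 with 20.
- Pre-product rate 3: from (3×5 + 10)/15 = 1.67 to (3×20 + 10)/30 = 2.33.
- Pre-product rate 5: from (5×5 + 10)/15 = 2.33 to (5×20 + 10)/30 = 3.67.

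Restricting to on-product years returns 1.0 in every case. If the rate did not differ before the product, nothing is distorted.

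**The case against.** The strongest reply is that index dates, on-product person-years and switch handling are normal SAP content, and the SAP is not shown. The lifetime sentence is general, bleeds are collected yearly so any window can still be cut, and the study promises a description of a population, not an on-product rate or a comparison. A lifetime view also suits joint damage, which shares an objective with bleeds.

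Part of this stands. Lifetime reporting is sound for joint damage and should be kept. The mismatch in the bleed-treatment objective is a risk and not a stated plan. The amendment clause is also weaker support than it looks: section 6 names primary objectives, no primary endpoint is designated, and adding a summary beside the lifetime one is not clearly a major modification.

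The main point survives. The protocol does not leave the outcome window open; it fixes it as lifetime and contrasts it with shorter windows for treatment. The SAP may change that, but the rule in the protocol remains ill suited to describing bleeds in product cohorts, and 7.10 does not disclose the consequence.

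Two further objections are fair. The percentages are shares of calendar time under chosen registration years, not estimates of bias. The change also needs some data specification beyond rewording, as set out under the fix.

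**Conclusion.** The concern holds. As written, bleeds described for the BeneFIX and ReFacto/ReFacto AF cohorts can include years before authorization and years on other products.

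The size cannot be determined from the protocol. In the illustration, the share of register time before authorization runs from nil for a patient registered in 2005 to 52-54% (BeneFIX) or 57-58% (ReFacto) for one registered in 1977. A product start later than authorization raises it, to 72-73% for a 1977 registration with an assumed start on 1 January 2005. These figures rest on the assumed registration dates, product start and end of follow-up. Any effect on the bleed rate also depends on how far bleeding differed before the product, which the protocol does not report.

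This should be fixed. It affects the descriptive bleed summary under a primary objective and does not undermine the rest of the description.

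**What to change.** - **Section 7.8, main change:** report bleeds in each product cohort as annualized rates over patient-years on the product, counted from the first prescription of that product and excluding time on other products. Keep the lifetime bleed and joint history beside it, labelled as patient history.
- **Section 7.8, safeguard:** state that bleeds are related to treatment only within the same patient-years, from 2005 when dispensing data are used. This guards against a possible misuse and is secondary to the main change.
- **Section 7.4:** list the product and prescription date from the Malmö register, which the selection in 7.2 already relies on, so that on-product years before 2005 can be identified.
- **Section 7.10:** state that lifetime outcomes include pre-product and off-product years.

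The cost is rewording of three sections and programming. No new data source is needed, since yearly bleeds, calendar-year consumption and dated dispensings are already in 7.4. Years containing a switch need an allocation rule, and bleeds counted at the yearly evaluation must be aligned with calendar-year consumption; both can go in the SAP. The downside is fewer patient-years in the on-product summaries, in groups of about 40 and 20 patients. The lifetime description loses nothing.

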7.9. Quality control

The information in the MHR is of highest quality. The coverage in the register is 100 percent for the patients that are diagnosed with hemophilia and treated at the MHC. Quality control in the MHR is rigorous. Each data point is checked to ensure the high quality.

Information for the selected patients in the register will be complemented by information from medical records when deemed necessary. This is done by the MHC. Quality control in the process is rigorous. Each data entry is checked to ensure the high quality.

The information from the MHR will further be record-linked with information on relevant drugs prescribed and picked up at a Swedish pharmacy. Prescription records and information on what prescriptions that were actually picked up at the pharmacy are available in the prescribed drug register at the NBHW since 2005. The only exception is when a patient must be given emergency treatment at another hospital than SUS. The linking of data will be carried out at the MHC. Data will be treated with privacy and according to the Swedish Personal data act.

Data management carried out by the vendor will be tracked so that data editing and other data corrections in the preparation of the analysis data sets will be transparent.

